**Incomplete/missing data:**

- Imputation rules for missing prior/concomitant medications, non-study vaccinations and procedures are provided in [Appendix C](#).
- Imputation rules for missing AE dates are provided in [Appendix D](#).
- For laboratory assessments, if majority of results are indefinite, imputation of these values will be considered. If the laboratory results are reported as below the LLOQ (e.g., <0.1), the numeric values will be imputed by  $0.5 \times \text{LLOQ}$  in the summary. If the laboratory results are reported as greater than the ULOQ (e.g., >3000), the numeric values will be imputed by ULOQ in the summary.
- Other incomplete/missing data will not be imputed, unless specified otherwise.

**Treatment groups:**

The following vaccination groups will be used for summary purposes:

- Part 1, Open-Label Phase:
  - mRNA-1273 vaccine 25  $\mu\text{g}$
  - mRNA-1273 vaccine 50  $\mu\text{g}$
  - mRNA-1273 vaccine 100  $\mu\text{g}$

- mRNA-1273 vaccine Total
- Part 2, Blinded Phase:
  - Treatment in Part 2 will be the selected dose level in each of the age groups from Part 1 or Placebo
    - mRNA-1273 vaccine 25 µg, or
    - mRNA-1273 vaccine 50 µg, or
    - mRNA-1273 vaccine 100 µg
  - And
  - Placebo

Subjects in an age group who received at least one dose of mRNA-1273 in Part 2 will be included in the mRNA-1273 selected dose level group (as actual treatment) for that age group in Part 2 in the safety analyses.

#### **Summary by age group:**

All analyses and data summaries/displays will be provided by vaccination group for each age cohort (6 months to < 2 years, 2 years to < 6 years, and 6 years to < 12 years), unless otherwise specified. Participants in Part 1 and 2 of the study and in different age groups who receive the same mRNA-1273 dose level may be combined for safety analysis.

#### **Summary by study part:**

Separate shells will be provided for Part 1 and Part 2 of the study. In Part 1, all analyses and data summaries/displays will be provided by age and vaccination group. In Part 2, all analyses and data summaries/ displays will be provided by age and vaccination group.

#### **Analysis Periods**

The following analysis periods and treatment groups will be used for efficacy analyses for Part 2, the blinded phase, unless specified otherwise:

| Part 2 Group | Description  | Part 2 Blinded Phase Analysis Period for Efficacy  |
|---------------------|---|---|
| mRNA-1273           | Participants randomized to mRNA-1273 in the Blinded Phase | From randomization to the earliest date of unblinding (date on Participant Decision Visit / Crossover Day 1 or unblinding day) inclusive, |
| Placebo             | Participants randomized to Placebo in the Blinded Phase   |   |

|  |  |  |
|--|--|--|
|  |  | study discontinuation, study completion, death, and data cutoff date |
|--|--|--|

Immunogenicity data at Day 57 are analyzed regardless of participant unblinding status at Day 57. The analysis period for efficacy specified above will not be applied to immunogenicity analysis. Since immunogenicity samples are handled and tested in a blinded manner and lab testing results are objective which are not impacted by unblinding status in individual participants. Therefore, the immunogenicity data at Day 57 after participant unblinding can still be included for the Day 57 immunogenicity analysis.

The following analysis period and treatment groups will be used for safety analysis for Part 2, the blinded phase, unless specified otherwise:

| Part 2 Group | Description   | Part 2 Blinded Phase Analysis Period for Safety  |
|--------------|---|--|
| mRNA-1273    | Participants received at least one dose of mRNA-1273 in the Blinded Phase | From the date of 1 st injection to the earliest date of unblinding (date on Participant Decision Visit / Crossover Day 1 or unblinding day) exclusive, study discontinuation, study completion, death, and data cutoff date |
| Placebo      | Participants only received Placebo in the Blinded Phase                   | From the date of 1 st injection to the earliest date of unblinding (date on Participant Decision Visit / Crossover Day 1 or unblinding day) exclusive, study discontinuation, study completion, death, and data cutoff date |

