### **6.5.2. Analysis Method**

The number and percentage of subjects who had an event (i.e. the first asymptomatic SARS-CoV-2 infection) will be summarized in the PP set for Efficacy.

The incidence rate will be provided by age and vaccination group, calculated as the number of cases divided by the total person-time. The 95% CI of the incidence rate will be calculated using the exact method (Poisson distribution) and adjusted by person-time.

Person-time is defined in Part 2 as the total time from randomization date to the date of event, last date of study participation, censoring time, or efficacy data cutoff date, whichever is earlier. For Part 1, switch randomization date to date of first injection.

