## **5.3. Per-protocol (PP) Immunogenicity Subset**

### Per-protocol (PP) Immunogenicity Subset (Long-term Analysis)

Per-Protocol (PP) Immunogenicity Subset (Long-term Analysis) at Day 1, Day 57 and Day 209 consists of all participants in Immunogenicity Subset (Long-term Analysis) who meet all the following criteria:

- a) Received planned doses of study vaccination per schedule
- b) Complied with the timing of second dose of injection
- c) If participants have a diagnosis of HIV, they are not receiving highly active anti-retroviral therapy (HAART)
- d) Had a negative SARS-CoV-2 status at baseline (pre-dose 1 of mRNA-1273)
- e) Had no major protocol deviations that impact key or critical data

The PP Immunogenicity Subset (Long-term Analysis) will serve as the population for the long-term analysis of immunogenicity data.

Per-protocol (PP) Immunogenicity Subset (Part 3, First Two Doses of Primary Series)

Per-Protocol (PP) Immunogenicity Subset consists of all participants in Part 3 Immunogenicity Subset who meet all the following criteria:

- a) Received planned doses of IP per schedule
- b) Complied with the immunogenicity window based on 2nd dose injection timing
- c) If participants have a diagnosis of HIV, they are not receiving highly active anti-retroviral therapy (HAART)
- d) Had baseline (Day 1) and Day 57 Ab assessment for the analysis endpoint
- e) Had no major protocol deviations that impact key or critical data

The PP Immunogenicity Subset will serve as the primary population for the analysis of immunogenicity data in this study unless specified otherwise. Participants will be analyzed according to the treatment group for the treatment which they actually received in Part 3.

Per-protocol (PP) Immunogenicity Subset (Booster/Third Dose Analysis)

Per-Protocol (PP) Immunogenicity Subset consists of all participants in Immunogenicity Subset for Booster/Third Dose Analysis who meet all the following criteria:

For mRNA-1273 Booster Dose:

- a) Received 2 doses of planned doses of mRNA-1273 vaccination in Part 1 open-label phase or Part 2 blinded phase per schedule
- b) Received booster dose in Booster Dose Analysis

- c) If participants have a diagnosis of HIV, they are not receiving highly active anti-retroviral therapy (HAART)
- d) Had a negative SAS-CoV-2 status at baseline (pre-dose 1 of mRNA-1273 )
- e) Had BD-Day 29 Ab assessment for the analysis endpoint
- f) Had no major protocol deviations that impact key or critical data

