- g) Not receive off-study COVID-19 vaccination prior to BD-Day 29 visit

For mRNA-1273 Third Dose:

- a) Received first 2 doses of planned doses of mRNA-1273 vaccination in Part 3 open-label phase per schedule
- b) Received third dose in Third Dose Analysis
- c) If participants have a diagnosis of HIV, they are not receiving highly active anti-retroviral therapy (HAART)
- d) Had BD-Day 29 Ab assessment for the analysis endpoint
- e) Had no major protocol deviations that impact key or critical data
- f) Not receive off-study COVID-19 vaccination prior to BD-Day 29 visit

The PP Immunogenicity Subset for Booster/Third Dose analysis will serve as a population for the analysis of immunogenicity in booster/third dose by pre-booster SARS-CoV-2 status (negative vs. positive).

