### **Analysis periods**

The following analysis periods and treatment groups will be used for long-term and booster dose analysis.

- Long-term Analysis (Part 1 Open-Label Phase plus Part 2 Blinded and Open-Label Phase, until Booster Dose)

| Group               | Category                    | Start Date                      | End Date  |
|---------------------|-----------------------------|---------------------------------|---|
| mRNA-1273           | Safety                      | Date of First Dose of mRNA-1273 | Earliest date of booster dose (exclusive), study discontinuation, study completion, death, or data cutoff |
| Placebo - mRNA-1273 |                             |                                 | Earliest date of booster dose (inclusive), study discontinuation, study completion, death, or data cutoff |
| mRNA-1273           | Efficacy/
Immunogenicity | Date of First Dose of mRNA-1273 | Earliest date of booster dose (inclusive), study discontinuation, study completion, death, or data cutoff |
| Placebo - mRNA-1273 |                             |                                 | Earliest date of booster dose (inclusive), study discontinuation, study completion, death, or data cutoff |

- Long-term analysis (Part 1 Open-Label Phase plus Part 2 Blinded and Open-Label Phase, Regardless of Booster Dose) incidence rate will also be performed for the entire study period after the first dose of mRNA-1273 regardlesss of booster dose.

| Group               | Category                    | Start Date                      | End Date  |
|---------------------|-----------------------------|---------------------------------|---|
| mRNA-1273           | Safety                      | Date of First Dose of mRNA-1273 | Earliest date of study discontinuation, study completion, death, or data cutoff |
| Placebo - mRNA-1273 |                             |                                 | Earliest date of study discontinuation, study completion, death, or data cutoff |
| mRNA-1273           | Efficacy/
Immunogenicity | Date of First Dose of mRNA-1273 | Earliest date of study discontinuation, study completion, death, or data cutoff |
| Placebo - mRNA-1273 |                             |                                 | Earliest date of study discontinuation, study completion, death, or data cutoff |

- Part 3, First Two Doses of Primary Series Analysis

| Group           | Category | Start Date                      | End Date  |

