|-----------------|----------|---------------------------------|---|
| mRNA-1273 25 µg | Safety   | Date of First Dose of mRNA-1273 | Earliest date of third dose (exclusive), study discontinuation, study completion, death, or data cutoff |

|                 |                |                                 |   |
|-----------------|----------------|---------------------------------|---|
| mRNA-1273 25 µg | Immunogenicity | Date of First Dose of mRNA-1273 | Earliest date of third dose (inclusive), study discontinuation, study completion, death, or data cutoff |
|-----------------|----------------|---------------------------------|---|

- Booster/Third Dose Analysis

| Group                                       | Category                | Start   | End   |
|---|-------------------------|---|---|
| mRNA-1273 - mRNA-1273 Booster               | Safety                  | Date of Booster/Third Dose  | Earliest date of study discontinuation, study completion, death, or data cutoff |
| mRNA-1273 - mRNA-1273 Third Dose            |                         |   |   |
| Placebo - mRNA-1273 - mRNA-1273 Booster     |                         |   |   |
| mRNA-1273 - mRNA-1273.214 Booster           |                         |   |   |
| Placebo - mRNA-1273 - mRNA-1273.214 Booster |                         |   |   |
| mRNA-1273 - mRNA-1273 Booster               | Efficacy/Immunogenicity | Date of Booster/Third Dose (considered as pre-booster/third dose data, exclusive) | Earliest date of study discontinuation, study completion, death, or data cutoff |
| mRNA-1273 - mRNA-1273 Third Dose            |                         |   |   |
| Placebo - mRNA-1273 - mRNA-1273 Booster     |                         |   |   |

For mRNA-1273.214 Booster Dose, only safety analysis related to endpoints in section 3.3.1 will be performed.

For Part 3 mRNA-1273 Third Dose, only safety and immune analysis related to endpoints in section 3.3 will be performed.

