6. Post-dosing, participants will have a 30-minute observation period. If any concerning symptoms occur, investigator may check vital signs during this period (however, no routine vital signs necessary after vaccination, except temperature as per 30-minute eDiary, if no concerning symptoms).
7. An unscheduled visit may be prompted by reactogenicity issues or new or ongoing AEs.
8. The nasal swab sample must be collected prior to injection at the BD-1 visit.
9. Trained study personnel will call all participants to collect information relating to any unsolicited AEs, MAAEs (including any signs and symptoms of COVID-19), AESI, AEs leading to withdrawal, SAEs, information on concomitant medications associated with those events, and any nonstudy vaccinations.
10. Age at time of enrollment determines which eDiary the participant will use. Diary entries will be recorded by the participant at approximately 30 minutes after injection while at the study site with instruction provided by study staff. Study participants will continue to record entries in the eDiary each day after they leave the study site, preferably in the evening, on the day of injection and for 6 days following injection. If a solicited local or systemic AR continues beyond Day 7 after vaccination, the participant will be prompted to capture details of the solicited local or systemic AR in the eDiary until the AR resolves; capture of details of ARs in the eDiary should not exceed 28 days after vaccination. Adverse reactions recorded in eDiaries beyond Day 7 should be reviewed either via telephone call or at the following study visit. Review of eDiary will occur on BD-D8 and BD-D29.
11. All concomitant medications relevant to or for the treatment of an SAE, AESI, or MAAE will be recorded from screening through the final visit. Non-study COVID-19 vaccines will be recorded through EOS.

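### Persistence summaries keep antibody samples taken after an off-study COVID-19 vaccination, and the incidence rules do not say whether that vaccination ends follow-up

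*SAP*

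**What the plan says.** The file holds two plans: the SAP for Part 1 and the Part 2 blinded phase (below, the blinded-phase SAP), and the SAP for the Part 2 open-label phase, booster doses and Part 3 (below, the long-term/booster SAP).

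**Analysis periods (section 6.1 of each).**
- Blinded-phase efficacy runs "From randomization to the earliest date of unblinding (date on Participant Decision Visit / Crossover Day 1 or unblinding day) inclusive", followed by "study discontinuation, study completion, death, and data cutoff date".
- The long-term efficacy and immunogenicity period, in the version that stops at the booster, ends at "Earliest date of booster dose (inclusive), study discontinuation, study completion, death, or data cutoff". A second version, for incidence, runs regardless of booster.
- The booster and third-dose period ends at "Earliest date of study discontinuation, study completion, death, or data cutoff".

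**Person-time (section 6.5.2).** In the blinded-phase SAP it ends at the event or at "last date of study participation, censoring time, or efficacy data cutoff date, whichever is earlier". The long-term/booster SAP also has a censoring time and adds the date of the next part's dose. Neither SAP defines the term.

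**Immunogenicity sets (long-term/booster SAP, section 5.3).** The booster and third-dose per-protocol subsets carry the criterion "Not receive off-study COVID-19 vaccination prior to BD-Day 29 visit". The long-term subset has five criteria and none concerns outside vaccination. Of that subset the SAP says: "The PP Immunogenicity Subset (Long-term Analysis) will serve as the population for the long-term analysis of immunogenicity data".

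**Data collection.** In the mRNA-1273 booster schedule (Appendix F, footnote 11), "Non-study COVID-19 vaccines will be recorded through EOS". The mRNA-1273.214 schedule (Appendix J) says the same. The safety calls in the primary-series schedule also ask about nonstudy vaccinations.

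**The concern.** The plan treats one biological event in three ways. A study booster ends the main long-term period. An outside dose before BD-Day 29 removes a child from the booster or third-dose per-protocol subset. An outside dose at any other time has no stated consequence, although later timepoints leave more time for one to occur.

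The antibody persistence endpoints are most affected: geometric means at Day 209 and Day 394 (blinded-phase SAP, section 3.2) and at BD-Day 181 and BD-Day 366 (long-term/booster SAP, section 3.3.3). A child who takes an outside dose and is then bled contributes a freshly boosted titre to a figure that will be read as waning after the study regimen.

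For incidence, person-time after an outside dose may stay in the group the child started in. Two programmers could compute different rates from the same data, depending on how each reads the undefined censoring time.

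**Working it through.** **1. Text check.** Each rule that could remove follow-up or samples after an outside COVID-19 vaccination:

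| Rule | Outside COVID-19 vaccination named? |
|---|---|
| Blinded efficacy period (6.1) | No |
| Long-term period, until booster (6.1) | No; the study booster is named |
| Booster/third-dose period (6.1) | No |
| Censoring time in person-time (6.5.2, both SAPs) | Undefined |
| mITT1 (blinded-phase SAP 5.9) | No; concerns doses other than as randomized or planned |
| PP Set for Efficacy; PP Immunogenicity Subset (blinded-phase SAP 5.3, 5.5) | No; general major-deviation clause |
| Long-term PP Immunogenicity Subset (5.3) | No; general major-deviation clause |
| Booster/third-dose PP Immunogenicity Subset (5.3) | Yes, before BD-Day 29 only |

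The major-deviation rules are left to be written before database lock (section 6.2.6 of each SAP). The visit windows in Appendix B give no protection: Day 394 takes any study day from 302 onward, and BD-Day 366 any day from 275 onward.

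**2. Effect on a geometric mean.** The plan states no figure to reproduce and gives no uptake or fold-rise, so both inputs are assumptions. Let f be the share of sampled children with an outside dose before the draw, and R the factor by which that dose raises their titre. The mean log titre rises by f × ln R, so the geometric mean is multiplied by R^f.

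| R | f = 2% | f = 5% | f = 10% | f = 20% |
|---|---|---|---|---|
| 5 | 1.03 | 1.08 | 1.17 | 1.38 |
| 10 | 1.05 | 1.12 | 1.26 | 1.58 |
| 20 | 1.06 | 1.16 | 1.35 | 1.82 |

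For example, 10^0.10 = 1.26. If later samples are excluded, f = 0 and the factor is 1.00.

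**3. Effect on the placebo rate.** Let f now be the share of blinded placebo person-time that follows an outside dose, and VE the protection that dose gives. The placebo rate is multiplied by 1 − f × VE:
- f = 2%, VE = 30%: 1 − 0.02 × 0.30 = 0.994
- f = 10%, VE = 50%: 1 − 0.10 × 0.50 = 0.95
- f = 20%, VE = 80%: 1 − 0.20 × 0.80 = 0.84

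This applies only to children vaccinated outside while still blinded, and only if the censoring time is not read to cover them.

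**The case against.** **Unblinding protects the placebo arm.** A reader might infer that every placebo child vaccinated outside the study stays in the placebo group. The documents do not support that. Unblinding ends the blinded efficacy period. Section 4.4 refers unblinding and cross-over after an authorization to protocol section 3.3, which is not at hand, and makes children under 6 eligible for unblinding six months after Dose 2. Only outside vaccination before unblinding counts. Unblinding gives no protection to the long-term and booster analyses, which continue after it.

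**The lists are not fully closed.** The blinded-phase table applies unless specified otherwise, and person-time includes a censoring time. For incidence the supportable criticism is that the term must be defined. It cannot remove an antibody sample.

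**Deviation rules may exclude these children.** They may, but the rules are not yet fixed. mITT1 has no deviation clause, and it is the primary set for endpoints from 14 days after the first dose and the set for long-term and booster incidence.

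**Incidence is secondary or exploratory.** This stands. Long-term and booster incidence is exploratory and is not calculated after October 2022. The plan gives rates with exact intervals and defines no vaccine-efficacy estimate, so a claim that efficacy is understated by some number of points measures something not planned.

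**Follow-up regardless of extra doses is a legitimate choice.** It is, and the plan provides one such incidence version. Families who seek an outside dose may also differ in exposure, so censoring there can be informative, and the net direction for incidence is not certain. But the version that stops at the booster aims to isolate the study regimen and does so only for study doses.

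**Few late booster samples may be affected.** Appendix G assigns BD-Day 181 and BD-Day 366 draws to Sub-Cohort D blocks (about 600 children each) separate from the block drawn at BD-Day 29, while the booster subset requires a BD-Day 29 result. Read strictly, this limits the late booster samples that reach the summary. In Part 3 both sub-cohorts have the Day 177 (BD-Day 29) draw, so the point applies there directly, though to at most the 91 children enrolled.

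It is also tempting to say that Part 2 children under 6 are the most exposed because they had no study booster before Amendment 9. That depends on when outside vaccines reached them, which the documents do not state.

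**Conclusion.** The point holds for antibody persistence. As written, Day 209/394 and BD-Day 181/366 samples taken after an outside COVID-19 dose are summarised as persistence of the study regimen, and this would raise the geometric means. Under assumed uptake of 2% to 20% and assumed 5- to 20-fold rises, the factor is about 1.03 to 1.82. The actual size depends on uptake, which the documents do not give.

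For incidence it holds in a weaker form: the period tables omit the event and the censoring time is undefined, so person-time after an outside dose may stay in the original group.

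A reader might infer that the noninferiority results are at risk. The documents do not show that: the booster coprimary analysis at BD-Day 29 already excludes outside vaccination, and no primary conclusion is shown to change. The correction is still worth making, because the plan applies the needed rule at one timepoint and omits it at the later ones.

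**What to change.** 1. In section 5.3 of the long-term/booster SAP, apply the existing exclusion at sample level: drop antibody samples taken after the first off-study COVID-19 vaccination at every long-term, post-booster and post-third-dose timepoint.
2. In section 6.1 of both SAPs, add the date of that vaccination to the efficacy end dates for the blinded period, the long-term period in its until-booster version, and the booster/third-dose period.
3. In section 6.5.2 of both SAPs, define the censoring time and include that date.
4. Keep the analysis regardless of off-study vaccination as a sensitivity analysis, because censoring at an outside dose may be informative.

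The cost is SAP wording and one derived date. Some late samples and person-time are lost, so intervals widen slightly. The booster schedules record outside COVID-19 vaccines through end of study. In the primary-series schedule, routine recording of nonstudy vaccinations covers only 28 days after each injection, so for children never boosted in the study the date rests on the safety calls. Check its completeness before lock.

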#### **4.4. Blinding and Unblinding**

This study is conducted in three parts, Part 1 of this study will be open label, blinding procedures will not be applicable.

Part 2 of this study will be conducted in an observer-blind manner. The investigator, study staff, study participants, study site monitors, and Sponsor personnel (or its designees) will be blinded to the IP administered until study end, with certain exceptions, please refer to Section 8.1 of the protocol for details.

Part 3 is open label; however, if blinded administration is ongoing at the site, blinded procedure for Part 2 still applies.

The final analysis of all endpoints will be performed after all participants have completed all planned study procedures.

At the time of interim analysis, only pre-identified Sponsor and unblinded Contract Research Organization (CRO) team members as specified in the study Data Blinding Plan will be unblinded to review treatment level results and individual listings. Please also refer to [Section 6.9](#). Study sites will remain blinded to individual treatment assignments until the end of the study.

If a COVID-19 vaccine is authorized or licensed for a specific age group before the end of the study, please refer to protocol section 3.3 for unblinding and/or cross-over plans.

Participants under 6 years of age in Part 2 who have reached at least 6 months follow up after Dose 2 will be eligible for unblinding via a telephone call to learn which treatment they received. Participants who received placebo will be offered the option of cross-over vaccination with mRNA-1273 at that point as described above.

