## 5.5. Per-Protocol (PP) Immunogenicity Subset

Per-Protocol (PP) Immunogenicity Subset consists of all participants in Immunogenicity Subset who meet all the following criteria:

- a) Received planned doses of IP per schedule
- b) Complied with the immunogenicity window based on 2nd dose injection timing
- c) Had a negative RT-PCR test for SARS-CoV-2 and a negative serology test based on bAb specific to SARS-CoV-2 nucleocapsid protein at baseline
- d) If participants have a diagnosis of HIV, they are not receiving highly active anti-retroviral therapy (HAART)
- e) Had baseline (Day 1) and Day 57 Ab assessment for the analysis endpoint
- f) Had no major protocol deviations that impact key or critical data

The PP Immunogenicity Subset will serve as the primary population for the analysis of immunogenicity data in this study unless specified otherwise. Participants will be analyzed according to the treatment group for the treatment which they actually received in Part 1 and to which they were randomized in Part 2.

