#### **6.4.3. Secondary Analysis of Antibody-Mediated Immunogenicity Endpoints**

For each group, the following evaluations will be performed at each time point at which blood samples are collected for immunogenicity (unless otherwise specified).

- GM level of anti-SARS-CoV-2-specific bAb with corresponding 95% CI will be provided at each time point. The 95% CIs will be calculated based on the t-distribution of the log-transformed values then back transformed to the original scale for presentation. The following descriptive statistics will be also provided at each time point: the number of subjects (n), median, minimum and maximum.
- GM fold-rise (GMFR) of SARS-CoV-2-specific bAb levels with corresponding 95% CI will be provided at each post-baseline timepoint over pre-injection baseline at Day 1. The 95% CIs will be calculated based on the t-distribution of the log-transformed values then back transformed to the original scale for presentation. The following descriptive statistics will be also provided at each time point: the number of subjects (n), median, minimum and maximum.

Proportion of subjects with fold-rise  $\geq 2$ , and fold-rise  $\geq 4$  of serum SARS-CoV-2 specific bAb levels from Visit Day 1 (baseline) at each post injection time points will be tabulated with 2-sided 95% Clopper Pearson CIs

- GMT of SARS-CoV-2-specific nAb values with corresponding 95% CI will be provided at each time point using the same method mentioned above.
- GMFR of SARS-CoV-2-specific nAb values with corresponding 95% CI will be provided at each post-baseline timepoint over pre-injection baseline at Day 1 using the same method mentioned above.

Proportion of subjects with fold-rise  $\geq 2$ , and fold-rise  $\geq 4$  of serum nAb from Visit Day 1 (baseline) at each post-injection time points will be tabulated with 2-sided 95% Clopper-Pearson CIs.

- Proportion of subjects with seroresponse due to vaccination will be tabulated with 2-sided 95% Clopper-Pearson CIs at each post-baseline timepoint. The definition of seroresponse can be found in [Section 3.1](#).

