## **5.2. Immunogenicity Subset**

### Immunogenicity Subset (Long-term Analysis)

Immunogenicity Subset for long-term analysis at Day 1, Day 57 and Day 209 consists of

- a) a subset of participants in the FAS (Long-term Analysis) and
- b) have baseline (pre-dose 1 of mRNA-1273) SARS-CoV-2 status available, and
- c) have baseline (pre-dose 1 of mRNA-1273) and at least one post-injection antibody assessment for the analysis endpoint.

Immunogenicity Subset for long-term analysis only includes subjects who received mRNA-1273 in Part 1 open-label phase and Part 2 blinded and open-label phase.

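### The blinded-phase SAP sets no immunogenicity cut at crossover, so placebo summaries, clearly at Day 394, may include samples taken after study mRNA-1273

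*SAP*

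**What the plan says.** Two plans are involved: the SAP for the Part 1 open-label and Part 2 blinded phases (the blinded-phase SAP), and the SAP for the Part 2 open-label phase, boosters and Part 3 (the long-term SAP).

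**Blinded-phase SAP**
- Section 6.1, Analysis Periods, defines the efficacy period: "From randomization to the earliest date of unblinding (date on Participant Decision Visit / Crossover Day 1 or unblinding day) inclusive", or an earlier discontinuation, completion, death or data cutoff. Safety has a similar cut.
- The same section then states "Immunogenicity data at Day 57 are analyzed regardless of participant unblinding status at Day 57" and "The analysis period for efficacy specified above will not be applied to immunogenicity analysis". The reason is that "lab testing results are objective which are not impacted by unblinding status in individual participants". No other end date for immunogenicity is given.
- Section 5.5 groups children in the PP Immunogenicity Subset by the treatment "actually received in Part 1 and to which they were randomized in Part 2". Section 5.4 also groups the Immunogenicity Subset as randomized.
- Section 4.4 makes Part 2 children under 6 years eligible for unblinding from 6 months after Dose 2: "Participants who received placebo will be offered the option of cross-over vaccination with mRNA-1273 at that point". For unblinding or crossover after a vaccine is authorized, it points to the protocol.
- Section 6.4.3 says that for each group "the following evaluations will be performed at each time point at which blood samples are collected for immunogenicity". Section 3.2 lists Day 209 and Day 394 GMs as secondary endpoints.

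**Long-term SAP**
- Section 6.1 places crossed-over children in a Placebo-mRNA-1273 group, whose immunogenicity period starts at the first mRNA-1273 dose.
- Section 5.2 says the long-term Immunogenicity Subset "only includes subjects who received mRNA-1273 in Part 1 open-label phase and Part 2 blinded and open-label phase".

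**The concern.** Knowing the treatment does not change a titre, so the stated reason justifies keeping a sample from a child who has merely been unblinded. It does not justify keeping a sample in the placebo column once the child has received mRNA-1273, and unblinding is the step that leads to that offer.

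No rule in the blinded-phase SAP separates the two cases. Two placebo doses given on schedule satisfy the dosing criterion of the PP Immunogenicity Subset, and no criterion refers to crossover before the sample. A placebo row at a late visit could then show antibody, and a rate labelled as seroresponse due to vaccination, that comes from the study vaccine. A reader could take it for background infection.

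**Working it through.** **Figures in the plan.** No stated figure turns on this point. The nearest is the placebo count in the Immunogenicity Subset, which reproduces from Table 2: 3 cohorts × 44 = 132 per age group.

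**Placebo samples that could be affected, per age group (Table 2).** Up to 132 at Day 57 (Cohorts A to C), 44 at Day 209 (Cohort B) and 44 at Day 394 (Cohort C). Cohort E adds 6 placebo children with exploratory samples at Days 209 and 394.

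**Earliest crossover, under 6 years.** Take Dose 2 on Day 29 and read 6 months as 180 to 184 days: 29 + 180 = Day 209, and 29 + 184 = Day 213.

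**Sampling times against that date** (Appendix E visit windows, Table 2 allowance and Table 5 analysis windows of the blinded-phase SAP):

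| Visit | Latest or range of sample day | Days relative to earliest crossover (Day 209 to 213) |
|---|---|---|
| Day 57, end of Table 5 window | 133 | 76 to 80 days before |
| Day 209, +14 days | 223 | up to 10 to 14 days after |
| Day 209, +30 days (Table 2) | 239 | up to 26 to 30 days after |
| Day 209, end of Table 5 window | 301 | up to 88 to 92 days after |
| Day 394, ±14 days | 380 to 408 | 167 (380 − 213) to 199 (408 − 209) days after |

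By visit:
- **Day 394:** a child who crosses over when first eligible is sampled about 167 to 199 days later. A child who accepts after the Day 394 draw is unaffected.
- **Day 209:** the 6-month route reaches it mainly through late or unscheduled samples. Crossover after an authorization could reach it more widely.
- **Day 57:** the 6-month route cannot reach it. Only crossover after an authorization, between placebo Dose 2 and the Day 57 draw, could do so in the PP subset. A child who crossed over before placebo Dose 2 would fail the PP dosing criterion but could remain in the Immunogenicity Subset.

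**Size, by assumption.** Let f be the share of placebo samples at a visit taken after crossover, s the proportion of those children meeting the seroresponse definition, and R the fold increase in titre. Neither f nor R is in the documents. For s, the range uses two figures from section 4.2: the planning rate of 85% and the 98.6% observed in young adults of Study P301.

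- Placebo seroresponse from crossover alone = f × s. At f = 0.10: 8.5% to 9.9%. At f = 0.25: 21% to 25%. At f = 0.50: 0.50 × 85% = 42.5% to 0.50 × 98.6% = 49.3%.
- Placebo GM is multiplied by R^f. At f = 0.50: 4^0.5 = 2.0, 20^0.5 = 4.5, 100^0.5 = 10.

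**Overlap of the two plans.** The long-term SAP assigns a post-crossover sample to Placebo-mRNA-1273, but nothing removes it from the as-randomized placebo column of the blinded-phase SAP. Within the long-term SAP, Table 4 gives windows for booster and Part 3 visits only, and Appendix B uses the nominal visit first. A nominal Day 209 or Day 394 result for this group therefore has no fixed time since crossover vaccination.

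**The case against.** The strongest reply is that the long-term SAP already handles these children. The blinded-phase SAP defines its analysis sets for the blinded phase and sends the open-label phase elsewhere, where crossed-over children have their own group from the first mRNA-1273 dose. This shows the likely intent, and it stands against any claim that the plan prescribes reporting vaccine antibody as placebo antibody. It does not close the gap. The only dates that end the Part 2 blinded phase are in the efficacy and safety tables of section 6.1, and neither applies to immunogenicity.

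A second reply is that the paragraph concerns Day 57, since the sentences around the quoted one name that visit. That is fair as to its purpose. But if the sentence is confined to Day 57, Days 209 and 394 still have no immunogenicity cut, because the table it refers to is for efficacy.

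Third, the crossover schedule in Appendix E of the long-term SAP lists no blood draw, and the protocol is not at hand. If draws stopped at crossover, the exposure would vanish. However, the long-term Immunogenicity Subset expressly takes in children given mRNA-1273 in the open-label phase who have a post-injection antibody result, so the plan expects such samples.

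A reader might also infer that all three visits are equally affected, or that a placebo-referenced persistence comparison is spoiled. The dates above rule out the first. On the second, the persistence objective concerns the response to mRNA-1273, and no section makes placebo its reference.

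**Conclusion.** The gap is real and limited. As written, the blinded-phase SAP allows samples taken after crossover mRNA-1273 into the placebo GM, fold-rise and seroresponse summaries. This is clear at Day 394, possible at Day 209, and possible at Day 57 only through crossover after an authorization. The same sample can also qualify for Placebo-mRNA-1273 in the long-term SAP, where its visit is not defined relative to crossover.

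Only descriptive placebo and Placebo-mRNA-1273 summaries are at risk. A reader might fear for the noninferiority conclusion, but the coprimary comparison sets mRNA-1273 children against P301 young adults and uses no placebo data.

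The size cannot be fixed from the documents. The figure of about 43% to 49% placebo seroresponse assumes that half the sampled placebo children had crossed over and that 85% to 98.6% of them meet the definition. A 100-fold titre increase should not be read into Day 209 samples drawn within two weeks of one crossover dose. Even a 4-fold increase in half the children would double the placebo GM.

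**What to change.** In section 6.1 of the blinded-phase SAP, keep the rule that Day 57 samples taken after unblinding without crossover are included. Add: *any immunogenicity sample taken after the first crossover dose of mRNA-1273 is excluded from the placebo group at all visits.*

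In the long-term SAP, assign Placebo-mRNA-1273 samples to visits by study day from crossover dosing, which section 6.1 already defines, and add the matching windows to Table 4. Alternatively, leave this group out of the nominal Day 209 and Day 394 summaries.

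The cost is SAP wording and one flag comparing the sample date with the first crossover dose date. No sample size or test changes. The drawback is fewer placebo samples at the late visits, where at most 44 per age group are scheduled in each of Cohorts B and C. The number excluded should be shown in the tables.
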